### 4.2 Study Design Rationale

#### 4.2.1 Study Population

Up to 25 healthy adult subjects presenting for abdominoplasty surgery will be enrolled and randomized. This will include a subset of up to 6 subjects with a history of hypertrophic or keloidal scarring. The full description of the inclusion and exclusion criteria is found in Section 5.

#### 4.2.2 Primary Effectiveness Outcome Measurements

The primary efficacy outcome parameter will be the difference in Patient and Observer Scar Assessment Scale (POSAS) scores, as assessed by the PI:

- 1) Between SLI-F06 treated excision sites and the vehicle treated excision sites at each timepoint during the Part A of the study;
- 2) Between the half of the abdominoplasty incision treated with SLI-F06 and the half of the incision treated with vehicle during Part B and Part B Extension of the study.

## 5 STUDY POPULATION

### 5.1 Inclusion Criteria

#### 5.1.1 Part A and Part B

The inclusion criteria below are only applicable to Parts A and B. Refer to Section 5.1.2 for the Inclusion Criteria for Part B Extension.

1. Outpatient, male or female of any race, 18 years of age or older. Female subjects of childbearing potential must have a negative UPT at Visit 1a (Study Part A) and 1b (Study Part B) and practice a reliable method of contraception throughout the study.

*A female is considered of childbearing potential unless she is:*

- *postmenopausal for at least 12 months prior to study treatment administration;*
- *without a uterus and/or both ovaries; or*
- *has been surgically sterile for at least 6 months prior to study treatment administration.*

*Reliable methods of contraception are:*

- *hormonal methods or intrauterine device in use ≥90 days prior to study treatment administration;*
- *barrier methods plus spermicide in use at least 14 days prior to study treatment administration; or*
- *vasectomized partner.*

*[Exception: Females of childbearing potential who are not sexually active are not required to practice contraception. These subjects may be enrolled at the site's PI's discretion if they are counseled to remain sexually inactive during the study or agree to use an approved method of contraception should they become sexually active and understand the possible risks in getting pregnant during the study.]*

2. Seeking or scheduled for standard elective abdominoplasty.
3. Willing to undergo directed excisions and follow-up prior to abdominoplasty and to undergo all follow-up visits after abdominoplasty.
4. Willing to undergo directed excisions under local anesthetic (i.e., does not require general anesthetic).
5. Be able to follow study instructions and likely to complete all required visits.
6. Sign the IRB-approved ICF (which includes the Photographic Release Form and HIPAA) prior to any study-related procedures being performed.

#### 5.1.2 Part B Extension:

The inclusion criteria below are only applicable to Part B Extension.

1. Current or previous participant in Part B of Study SLI-C40-001.
2. Sign the IRB-approved ICF (which includes the Photographic Release Form and HIPAA) prior to any study-related procedures being performed.

### 5.2 Exclusion Criteria

#### 5.2.1 Parts A and B

The Exclusion Criteria below are only applicable to Parts A and B. Refer to Section 5.2.2 for the Exclusion Criteria for Part B Extension.

1. Female subjects that are pregnant, breast-feeding, or of childbearing potential and not practicing reliable birth control (as specified in Section 5.1).
2. Known hypersensitivity or previous allergic reaction to any constituent of the IP (i.e., SLI-F06).
3. History of diabetes mellitus or an HgB A1C greater than 5.7 percent.
4. Morbid obesity (i.e., BMI >40).
5. History of prior abdominal surgery. *[Note: laparoscopic surgery that did not result in open laparotomy or routine cesarean section surgery is acceptable provided the procedure occurred at least 3 years prior to Visit 1a]*
6. History of abdominal liposuction, cryolipolysis, focused ultrasound or other fat reduction procedures in or near the anterior abdomen within 12 months of Visit 2a.
7. History of poor or delayed wound healing such as a prior wound dehiscence, chronic wound or leg ulcer.
8. History of or evidence of a genetic collagen disorder such as Ehlers-Danlos syndrome.
9. Operating Physician unable to design an abdominoplasty incision area of at least 25 cm wide by 12 cm tall at the center of the fusiform.
10. The presence of any abnormality of the skin within the area of the proposed abdominoplasty that, **in the opinion of the PI**, could interfere with the excision process or grading of the resultant surgical scar (e.g., striae gravidarum, striae distensae, excessive nevi, numerous seborrheic keratoses, tattoos, etc.).
11. Use of any concomitant medications/procedures or tobacco/inhaled nicotine products specified in Section 6.7.1 within a restricted time period.
12. Allergy to or intolerance of local anesthetics.
13. Medical or psychiatric conditions that may increase the risk associated with study participation or may interfere with interpretation of study results or compliance of the subject and, **in the opinion of the PI**, would make the subject inappropriate for study entry.
14. Any personal, familial, employment or financial situation that could impede the subject's ability to attend all study visits and successfully complete the entire clinical study.
15. Clinically significant alcohol or drug abuse, or history of poor cooperation or unreliability.
16. Exposure to any other investigational drug/device within 30 days prior to study entry.

### **5.2.2 Part B Extension**

The Exclusion Criteria below are only applicable to Parts B Extension.

1. None

### **5.3 Subject Withdrawal Criteria**

Reasons for withdrawal may include, but are not limited to, the following:

- At the request of the PI or study Sponsor (e.g., for tolerability reasons, SAE, etc.).
- At the request of the subject.
- When the requirements of the protocol are not followed.

- When a concomitant therapy or interventional surgery required by the subject is likely to interfere with study results, (report all such information on the source documents and CRFs) and confer with the Sponsor if the subject should be withdrawn).
- When a subject is lost to follow-up. The PIs will try at least twice to reach the subject by telephone and document these attempts and then send a follow-up letter by certified mail before considering that the subject is lost to follow-up.

All premature discontinuations and their reasons must be carefully documented by the PI in the source documents, CRF, and (if applicable), on the AE form.

No subject who has received study injection(s) can be replaced if they discontinue prematurely for whatever reason. All data gathered on the subject prior to termination will be made available to the Sponsor.

Reasons for study completion/discontinuation as listed on the final report form are defined as follows:

- **Normal Study Completion** – Subject completes the study as planned in the protocol.
- **Adverse Event** – Complete AE form.
- **Death** – Complete SAE form.
- **Subject Request** – Consent withdrawal, subject moved, schedule conflicts.
- **Protocol Violation** – Contact the Sponsor or designee before making decision.
- **Lost to Follow-Up** – Document with 2 phone calls and a certified letter.
- **Pregnancy** – Subject will discontinue study drug immediately, but will be followed to term. Complete pregnancy form.
- **Study Terminated by Sponsor**
- **Other** – Specify in comments section of final CRF.

Subjects are free to withdraw from participating in this study at any time and for whatever reason, specified or unspecified, and without prejudice.

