**Table 1. Prohibited medications and procedures**

Description	Washout Period
• Systemic corticosteroids (e.g., prednisone, triamcinolone, etc.) [NOTE: inhaled and insufflated corticosteroids of stable dosing are acceptable]	4 weeks
• Topical corticosteroids in or around the treatment areas [NOTE: low/medium potency corticosteroids may be used in areas removed from the treatment area with caution to ensure no contamination of the treatment area]	4 weeks
• Antimetabolite medications (e.g., methotrexate, azathioprine, 6-mercaptopurine, etc.)	8 weeks
• Antineoplastic agents	4 weeks
• Chronic NSAID use (i.e., use for more than 7 days out of the prior 14 days) [NOTE: short courses of NSAIDS are allowable to manage acute pain/inflammation syndromes but should be limited to 7 days or less]	4 weeks
• Oral hypoglycemic agents or any form of insulin	2 years
• Agents that prolong bleeding times (i.e., coumarin, heparin, clopidogrel, Factor Xa inhibitors, vitamin E supplementation $\geq$ 30,000 IU per day, etc.)	4 weeks
• Investigational drug or device	30 days
• Tobacco/inhaled nicotine products (cigarettes, pipe, snuff, cigars, vaporizers)	6 months
• Incisional surgery of any kind from the level of the umbilicus to the knees	12 months
• Any cosmetic surgery (e.g., facelift, breast enhancement, etc.).	Prohibited during study Parts A and B (Not applicable to Part B Extension)

All treatment/procedures received by the subject within 30 days prior to Visit 1a and throughout the treatment period, including the name of the treatment/procedure, must be recorded in the eCRF with end dates, if applicable. Use of prohibited treatment/procedures must be recorded in the eCRF up to the extent of the prohibited time period indicated above.

In the event such prohibited therapies are administered during the study period, the Medical Monitor will be contacted to discuss the details of the event. Subject participation will not automatically be discontinued. At a minimum, the event will be documented by the site staff as a protocol deviation, as instructed by the Medical Monitor. Depending upon the nature of the prohibited therapy and the timing relative to the determination of the primary endpoint, the Medical Monitor may make a decision to discontinue the subject.

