## **10.4 Analysis Populations**

### **10.4.1 Primary Population for Efficacy Analysis**

The ITT population will be the primary population for efficacy and safety analyses and will consist of all randomized subjects who received at least one injection of IP and provided at least one post-baseline evaluation, and will be analyzed in the treatment group they were allocated.

A per-protocol (PP) population will neither be identified nor analyzed.

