## **10.8 Missing Efficacy Data Imputations**

Data will be analyzed as observed; no imputations will be made for missing data.

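### Subjects already injected can be taken out of scheduled assessments for not following the protocol, so later visits may hold only those who were not removed, at odds with the stated ITT basis

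*Protocol*

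**What the plan says.** Section 5.3 of the protocol introduces its withdrawal reasons permissively: "Reasons for withdrawal may include, but are not limited to, the following". One of them is "When the requirements of the protocol are not followed". Another is a concomitant therapy or surgery likely to disturb the study results, to be discussed with the Sponsor. Neither is limited to subjects who have not yet been injected. Protocol Violation is also a formal reason for discontinuation, with the instruction "Contact the Sponsor or designee before making decision" but no criteria for the decision.

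The same section states "No subject who has received study injection(s) can be replaced if they discontinue prematurely for whatever reason". On data it provides only that "All data gathered on the subject prior to termination will be made available to the Sponsor".

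In section 6.8.1, the text after Table 1 says that prohibited therapy does not end participation automatically and is at least documented as a deviation. It then adds that, depending on the kind of therapy and on when it falls relative to the primary endpoint, "the Medical Monitor may make a decision to discontinue the subject".

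The analysis sections point the other way. Section 10.4.1 bases ITT on randomization, at least one injection and at least one post-baseline evaluation, with no adherence condition, and says "A per-protocol (PP) population will neither be identified nor analyzed". Section 10.8 says "Data will be analyzed as observed; no imputations will be made for missing data".

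**The concern.** Within a part, study treatment is given in one session: Visit 2a in Part A and Visit 1b in Part B. After that session, withdrawing a subject for non-adherence spares no further exposure in that part. Its main effect is that scheduled POSAS ratings, non-serious adverse event collection and antibody sampling stop.

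If the reason for removal is non-adherence or an interfering therapy, the subjects still rated at a late visit have been selected on adherence. An as-observed analysis of that visit is then close in effect to the per-protocol analysis that section 10.4.1 rules out, although it is reported under the ITT label. The selection could be related to outcome. For example, section 6.5.9 classes adhesive strip use after Part A suture removal as a protocol violation, and such use could plausibly follow poor healing.

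The trial is first-in-human (section 1), and safety is the primary objective of Parts A and B (section 2). Post-exposure data from about 25 subjects who cannot be replaced are therefore worth keeping.

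**Working it through.** **What happens to an injected subject withdrawn for non-adherence**

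| Question | Answer | Source |
|---|---|---|
| Can it happen after injection? | Yes, at discretion | 5.3, 6.8.1 |
| Is treatment left to stop in that part? | No; one session per part | 9.2.2, 9.3.1 |
| Does the subject stay in ITT? | Yes, given one post-baseline evaluation | 10.4.1 |
| Does the subject stay in the safety population? | Yes | 10.4.2 |
| Are earlier data kept? | Yes | 5.3 |
| Are later scheduled assessments provided for? | No; the schedule has no early-termination visit | 5.3, Study Summary |
| Is the subject replaced? | No | 5.3 |
| Are later values imputed? | No | 10.8 |
| Can a subject withdrawn in Part A enter Part B? | Part B is described for those who complete Part A | Synopsis, Study Design |

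The set on paper is therefore unchanged, but the set contributing to each later visit excludes those removed. A Part A withdrawal loses the remaining Part A assessments and the whole Part B pair.

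The protocol already separates stopping study drug from leaving follow-up in one case: under Pregnancy in section 5.3, study drug stops and the subject is followed to term.

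**Illustrative size for a late visit**

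The sample size of about 25 rests on the Sponsor's opinion (section 10.1), with no effect size, SD, power or dropout allowance. There is no figure to reproduce, and none is called wrong.

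Inputs:
- From the documents: n = 25 within-subject pairs per part; two-sided alpha 0.05 (section 10).
- Assumed: a paired t-test, 80% power, and 0, 3, 5, 7 or 10 pairs lost. Differences are in units of the SD of the within-subject difference.

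Formulas:
- Power = 1 − F(t; n − 1, d√n), where F is the noncentral t distribution function and t is the 0.975 quantile of Student's t on n − 1 degrees of freedom. The detectable difference is the d that gives 0.80.
- 95% CI half-width = t / √n.

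| Pairs at the visit | Detectable difference (SD) | Power at 0.584 SD | CI half-width (SD) |
|---|---|---|---|
| 25 | 0.584 | 80.0% | 0.413 |
| 22 | 0.626 | 74.3% | 0.443 |
| 20 | 0.660 | 69.8% | 0.468 |
| 18 | 0.701 | 64.7% | 0.497 |
| 15 | 0.778 | 55.8% | 0.554 |

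As a check, the normal approximation for 25 pairs gives 0.560, slightly below the exact 0.584, as expected. One lost pair is 1/25 = 4% of the information at that visit and takes power at 0.584 SD from 80.0% to 78.2%. Three lost pairs raise the detectable difference by 0.626/0.584 − 1 = 7%; five raise it by 0.660/0.584 − 1 = 13%.

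**The case against.** The case against is substantial, and much of it stands.

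- **The clause is discretionary.** The list in 5.3 is permissive, the Sponsor is contacted before a withdrawal for violation, and under 6.8.1 the minimum response to prohibited therapy is to document a deviation. That default is close to what is asked for here. But no criteria bound the discretion, and one stated consideration is timing against the primary endpoint, which concerns interpretability rather than subject safety.
- **A reader might infer that the ITT population itself becomes a per-protocol set.** It does not. Sections 10.4.1 and 10.4.2 set no adherence condition, and a withdrawn subject stays in with earlier data. The effect is confined to visits after withdrawal.
- **A reader might infer that the upper bound for an adverse event never observed gets worse.** For 25 exposed subjects with no events the one-sided 95% bound is 1 − 0.05^(1/25) = 11.3%. Withdrawal does not move it, because the safety denominator is everyone injected. What shrinks is observation time.
- **A reader might treat the injection as given once in the whole trial.** There are two separately randomized sessions, so leaving during Part A also ends planned exposure. The argument holds only within a part.
- **A reader might infer that safety follow-up is lost altogether.** Under 9.6.3.6, serious events are followed to resolution or stabilization even after a subject leaves, and related serious events learned of later are reportable. Under 9.6.3.2, clinically significant related events at the final visit are followed for up to 30 days. Routine non-serious event collection and antibody sampling would stop.
- **A reader might infer a bias between treatments.** Both halves of a pair leave together under blinding, so no side-to-side imbalance follows directly. The harm shown is lost precision and selection of who is seen late.
- **The Extension offers partial recovery.** It admits current or previous Part B participants with no exclusion criteria, so someone withdrawn before Month 12 could be rated from Month 15. The intervening ratings are still gone, and the Extension has no antibody sampling and records only treatment-related events.
- **The analysis plan could address handling.** As-observed analysis is not an error in itself, and sensitivity analyses belong in that plan. But who remains under observation is settled by protocol conduct, and no analysis plan can recover data never collected.

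**Conclusion.** The point holds in a limited form. Sections 5.3 and 6.8.1 allow an injected subject to be removed, at discretion, for reasons of adherence or interpretability. With no replacement, no continued scheduled assessments and as-observed analysis, later visits can be restricted to subjects who were not removed. That is at odds in effect, though not in literal wording, with the ITT basis and the rejection of a per-protocol set in section 10.4.1.

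The size is unknown, because the protocol gives no withdrawal rate. If 3 to 5 of 25 pairs were missing at a late visit for this reason, the detectable difference would rise by about 7% to 13%, and power at 0.584 SD would fall from 80.0% to between 74.3% and 69.8%. These figures rest on an assumed paired t-test, an assumed 80% power target and assumed losses. Nothing in the protocol suggests that non-adherence will cause that many withdrawals, and the study was not sized on power. No figure in the protocol is overturned. This is a cheap improvement worth making, not a defect that undermines the trial.

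**What to change.** Reconcile 5.3 and 6.8.1 with 10.4.1 and 10.8. State that, once a subject has been injected in a part, non-adherence or prohibited therapy is recorded as a deviation (or as a violation where section 11.3 so classifies it), and that the subject stays in the scheduled POSAS, adverse event and immunogenicity assessments of that part unless consent is withdrawn. Record leaving assessments separately from any decision about a later study injection; that decision is clinical and is not addressed here.

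The cost is a wording change, a few extra visits for subjects who would otherwise have been withdrawn, and possibly noisier late data. A sensitivity analysis without these subjects can show how much they matter.

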## 6 TREATMENT PLAN

### 6.1 Subject Numbering

Each screened subject will be assigned a unique 4-digit study subject number assigned by the investigational site, which will consist of a pre-assigned 1-digit investigational site number and a 3-digit chronological screening order number, starting with 001 (e.g., 1001, 1002). Subject Numbers will not be omitted or reused. Subjects withdrawn from the study will retain their Subject Number; new subjects will be allotted a new Subject Number.

### 6.2 Randomization

A hardcopy computer generated “Randomization Schedules” will link a bilateral (left, right) treatment assignment to each Subject Number (Section 6.1). Randomization to treatment assignment for Part A will be independent of Part B randomization. The Randomization Schedule will be maintained by the Independent Drug Reconstitutor (Section 6.3). During Part A, all excisions to be treated with SLI-F06 for a given subject will be on one side of the mapped area (i.e., left side or right side) and vehicle treated excisions will be on the other side of the mapped area. During Part B, one side of the abdominoplasty incision will be treated with SLI-F06 (i.e., left side or right side) and the other side of the incision will be treated with vehicle.

### 6.3 Blinding

To maintain study blind, the Independent Drug Reconstitutor (IDR) (i.e., pharmacist, study nurse or physician not responsible for subject follow-up) will have access to the Randomization Schedule, be aware of treatment assignment, and will prepare study medication. “Injectors”, Investigators, and study coordinators responsible for subject assessment and follow-up, and study subjects will remain unaware of which study treatment was injected on either side of the pannus or abdominoplasty incision, but might not be blinded to the degree of wound tension.

The IDR will consult the Randomization Schedule, prepare syringes of SLI-F06 and vehicle, and label syringes accordingly with the designation of “left side” or “right side”.

### 6.4 Unblinding

The treatment assignments for all enrolled subjects will be unblinded only after the conclusion of the study (or for interim analyses). Specifically, the blind will be broken only after all data are verified, entered into the database and validated, and the database is locked. If it is medically imperative to know what study treatment was injected on a particular side, the Investigator or authorized person will contact the IDR (or designee) to obtain the treatment assignment for that subject. Prior to unblinding, the investigator should attempt to contact the Medical Monitor and ethica CRO Inc. to discuss the rationale for unblinding. The rationale for breaking the code must be recorded in the subjects’ medical record and eCRF.

### 6.5 Pannus Excision Sites - Study Part A

#### 6.5.1 Excision Sites

Each excision site will be a 3 cm long fusiform excision. All excisions will be performed in an identical manner except for dimensions. Two types of fusiform excisions will be made (templates will be provided):

- **Low tension** wounds will have a 3 cm length with a maximum midpoint width of 1 cm;
- **High-tension** wounds will have a 3 cm length and a maximum midpoint width of 2 cm.

### 6.5.2 Pannus Map and Excision Template

The Investigator will assess the subject's abdomen (while supine) and will select the appropriate size of pannus map. If unable to select a suitable pannus map, the subject will be considered as a screen failure. The following sizes of pannus maps will be supplied to the site:

**Small pannus map:** For an abdominoplasty area of at least 25 cm length x 12 cm height. This map accommodates 6 small wounds (3 cm length x 1 cm width, green wounds) and 6 large wounds (3 cm length x 2 cm width, blue wounds) for a total of 12 wounds per subject. The excision sites will be numbered as shown in Figure 1 below:

[figure not shown]

Figure 1. Small Pannus Map

**Medium pannus map:** For an abdominoplasty area of at least 30 cm length x 14 cm height. This map accommodates 6 small wounds (3 cm length x 1 cm width, green wounds) and 8 large wounds (3 cm length x 2 cm width, blue wounds) for a total of 14 wounds per subject. The excision sites will be numbered as shown in Figure 2 below:

[figure not shown]
[figure not shown]

Figure 2. Medium Pannus Map

**Large pannus map:** For an abdominoplasty area of at least 32 cm length x 18 cm height. This map accommodates 8 small wounds (3 cm length x 1 cm width, green wounds) and 10 large wounds (3 cm length x 2 cm width, blue wounds) for a total of 18 wounds per subject. The excision sites will be numbered as shown in Figure 3 below:

